Wound Dressing in Patients with Hidradenitis Suppurativa: A Pilot Study

STUDY PROTOCOL
PROTOCOL NUMBER 20191046
NCT04194541

Principal Investigator:
[name]

[name] Department of Dermatology & Cutaneous Surgery, University of Miami Miller School of Medicine.

[contact] or [contact] (24-hour page operator)

Email Address: [contact]

Protocol Version No.3 Date: April 6, 2022

1) Objectives*

The primary purpose of this research is to determine how the types of wound dressings affect quality of life for people with Hidradenitis Suppurativa (HS). The secondary purpose is to evaluate the utility of a starter kit concept for wound care in people with HS.

1. Primary outcome: quality of life as measured by the DLQI instrument.
2. Secondary outcomes include:
 - a. Average pain as measured on NRS
 - b. Maximal pain as measured on NRS
 - c. Sleep assessment as measured on 5-point likert scale
 - d. Drainage assessment as measured on 4-point likert scale
 - e. Odor assessment as measured on 4-point likert scale
 - f. Patients' overall preference of dressings for HS as measured on a 5-point likert scale
 - g. Which dressings work best for which parts of the body as measured by patient log
 - h. Frequency of dressing changes required as measured by patient log
 - i. *HS-Physician's Global Assessment (HS-PGA)*
 - j.

Study Endpoints:

Primary endpoint	Change in DLQI from baseline to week 6
Secondary endpoint	Change in average pain NRS from baseline to week 6
Secondary endpoint	Change in maximal pain NRS from baseline to week 6
Secondary endpoint	Change in sleep rating from baseline to week 6
Secondary endpoint	Change in drainage rating from baseline to week 6
Secondary endpoint	Change in odor rating from baseline to week 6

Secondary endpoint	Overall dressing preference for HS as noted by subjects on patient log
Secondary endpoint	Dressing preference for body parts as noted by subjects on patient log
Secondary endpoint	Average frequency of dressing changes as noted by subjects on patient log
Secondary endpoint	Change in HS-PGA at 6 weeks after initial assessment

2) Background*

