Visit 2 will take place 28 +/- 3 days after visit 1. Subjects will follow up for an end of treatment visit where they will have a physical exam. Maximal and average pain will again be assessed on a 5-point likert scale. Quality of sleep, drainage, and odor will be assessed as well (Table 1). Photographs and measurements of HS wounds will be taken. Wound swab samples will be collected from the wound that was pre-identified at baseline visit. Subjects' medical records will be reviewed to collect medical history, treatment plans and disease progress. Please see Table 1 below detailing the schedule of events.

Finally, in order to correlate the above outcomes with independent disease progression, HS-PGA score will be calculated at visits 0, 1 and 2. The HS-PGA instrument is a 6-point scale used to assess overall disease severity. HS-PGA will

be completed at baseline and follow up visits (Table 1). HS affected areas will be evaluated and given a numerical score based on presence of abscesses, draining fistulas, inflammatory nodules, and non-inflammatory nodules. Then the points are added to create one global score. A 2 point reduction and above is considered a meaningful clinical response.

Assessments:

1. Maximal NRS:

Please rate your pain **at its worse** over the last 24 hours on the scale below.

2. Average NRS:

Please rate your pain **on average** over the last 24 hours on the scale below.

3. Drainage assessment:

How much did your lesion(s) drain during the past 24 hours?

No draining	A little draining	Moderate draining	A lot of draining
1	2	3	4

4. Sleep assessment:

How much was your sleep disturbed by HS last night?

Not at all	A little bit	Moderately	A great deal	Unable to sleep
1	2	3	4	5

5. Odor assessment:

How would you rate the odor caused by the draining of your lesion(s) during the past 24 hours?

No odor	A little odor	Moderate odor	A lot of odor
1	2	3	4

6. Dressing's ease of use assessment:

How easy to use are your current dressings?

Very Difficult	Difficult	Neutral	Easy	Very Easy
1	2	3	4	5

7. Dressing satisfaction:

How satisfied are you with your current dressings?

Strongly Dissatisfied	Dissatisfied	Neutral	Satisfied	Strongly Satisfied
1	2	3	4	5

8. HS-PGA:

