6.2 Dressing Logs and Photographs

The dressing logs and photographs collected from each patient will be de-identified and stored in a computer located in the Dermatology Research office. The computer

is located in a locked room in the University of Miami Hospital West Building, Room 506, [name].

Statistical analysis will be performed using software already available in the lab. This information will be protected in a locked office (see Confidentiality section below) and will only be able to be accessed by the primary investigator and the co-investigators. The photographs will then be downloaded as encrypted, de-identified JPEG/TIFF files and stored in the PI computers protected by login and password (see section 16).

6) **Data Management***

The investigator (or research staff) will record the data collected in a manner that does not include any direct identifiers of the subject. The investigator will assign a code to each subject and link the code to the subject's identity. The link to the subject's identity will be maintained on a document separate from the research data. Both documents will be stored on password-protected media on a University of Miami encrypted device. The data will be stored for at least 3 years after the study has concluded and will be destroyed at the earliest opportunity in accordance with University of Miami's policies thereafter. Data will only be accessed by designated study team members.

Statistical analysis of collected data will be performed using IBM SPSS Statistics for Windows (IBM Corporation, Armonk, NY, USA). Mean and range will be calculated for continuous variables. Pearson's chi-squared test will be used to test for independence between categorical variables; for expected values less than 5, Fisher's exact test of independence will be used.

Adverse Events

7) **Adverse Events***

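### No method is assigned to the aim of correlating outcomes with HS-PGA, and the only test the plan names ignores the order of the rating scales

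*Combined protocol and SAP*

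**What the plan says.** Section 4 (Procedures Involved) gives the purpose of HS-PGA: "in order to correlate the above outcomes with independent disease progression, HS-PGA score will be calculated at visits 0, 1 and 2". No statistical method follows, there or elsewhere.

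The scales involved are ordered. Section 1 (Objectives) lists "Sleep assessment as measured on 5-point likert scale", "Drainage assessment as measured on 4-point likert scale" and "Odor assessment as measured on 4-point likert scale", and its endpoint table defines each as a change from baseline to week 6. On HS-PGA, section 4 says "The HS-PGA instrument is a 6-point scale used to assess overall disease severity", with levels running from Clear to Very severe in Appendix Table 1. A little later it also says "Then the points are added to create one global score", which reads more like a numeric total.

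The whole analysis plan is one short paragraph in section 6 (Data Management). For continuous variables: "Mean and range will be calculated for continuous variables". For categorical variables: "Pearson's chi-squared test will be used to test for independence between categorical variables; for expected values less than 5, Fisher's exact test of independence" is to be used. The plan does not list which variables count as categorical. It names no rank correlation, trend test or ordinal model, and states no significance level, effect size or power.

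Section 14 (Local Number of Subjects) aims for 20 subjects from 30 enrolled.

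**The concern.** The question in section 4 is directional: do symptom ratings rise and fall with disease severity? Chi-squared and Fisher's test answer a different one. Both treat the levels as unordered labels, so shuffling the four drainage levels leaves the p-value unchanged, and neither shows which way an association runs.

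The study has no control group, and active wounds also receive standard care, including debridement when appropriate. The comparison with HS-PGA is the plan's stated means of setting changes in drainage, odor or sleep against the course of the disease. If the method actually used has little power, a non-significant result is likely even when the ratings do follow the disease, and it would say little either way.

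**Working it through.** **Plan's own figure.** There is no power calculation to reproduce. The only figures are 20 subjects reached from 30 enrolled, which implies a loss of 10/30 = 33%.

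**Step 1: which named test would apply.** The mean expected count is n / (rows × columns), and the smallest expected count cannot exceed the mean.

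- Drainage or odor by HS-PGA (4 × 6 = 24 cells): 20/24 = 0.83; 30/24 = 1.25.
- Sleep by HS-PGA (5 × 6 = 30 cells): 20/30 = 0.67; 30/30 = 1.0.
- Even with uniform margins, every expected count reaches 5 only at 5 × 24 = 120 or 5 × 30 = 150 subjects.
- With only a 3 × 3 table occupied, 30/9 = 3.3, still below 5.

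So if the ratings are treated as categorical, the plan's rule leads to Fisher's test.

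**Step 2: what the test looks for.** An order-blind test spreads over (4−1)(6−1) = 15 or (5−1)(6−1) = 20 degrees of freedom. A rank correlation uses 1.

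**Step 3: power.** The documents give no correlation, category frequencies or significance level, so these are assumptions: two-sided 5%, and two latent normal variables with a given correlation cut into ordered categories, with varied category frequencies. Each setting used 1,000 simulated datasets, with permutation p-values for the Fisher-Freeman-Halton and Spearman tests. Under no association both tests rejected in about 4–6% of datasets.

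| Table | n | Latent correlation | Fisher | Spearman |
|---|---|---|---|---|
| 4 × 6 (drainage or odor by HS-PGA) | 20 | 0.3 | 9% | 21% |
| | 20 | 0.5 | 17% | 52% |
| | 20 | 0.7 | 41% | 88% |
| | 30 | 0.3 | 10% | 29% |
| | 30 | 0.5 | 28% | 75% |
| | 30 | 0.7 | 64% | 98% |
| 5 × 6 (sleep by HS-PGA) | 20 | 0.5 | 16% | 53% |
| | 30 | 0.5 | 29% | 73% |
| 5 × 5 (change by change) | 20 | 0.5 | 15% | 52% |
| | 30 | 0.5 | 26% | 72% |
| 3 × 4 (few levels occupied) | 20 | 0.5 | 18% | 43% |
| | 30 | 0.5 | 35% | 65% |
| 3 × 3 (few levels occupied) | 20 | 0.5 | 24% | 42% |
| | 30 | 0.5 | 40% | 60% |

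Further full-scale runs at 0.5 with other category frequencies gave 12–15% against 49–52% at n = 20, and 22–26% against 69–73% at n = 30. Taken together, the full-scale range at 0.5 is about 12–29% against 49–75%. In the 3 × 3 table the gap falls to 42 − 24 = 18 points (n = 20) and 60 − 40 = 20 points (n = 30).

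**Step 4: share missed.** Among datasets where Spearman was significant on the full 4 × 6 and 5 × 6 tables, Fisher was not significant in:

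- 65–86% at correlations of 0.3–0.5;
- 53–70% at 0.6;
- 54–60% (n = 20) and 35–39% (n = 30) at 0.7;
- 35–42% (n = 20) and 12–16% (n = 30) at 0.8.

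**Step 5: limits of the rank method.** At a correlation of 0.3 its own power was only 17–30%. An approximate 95% interval, ignoring ties, is tanh(atanh r ± 1.96/√(n−3)). For an observed r of 0 this is ±tanh(1.96/√17) = ±0.44 at n = 20 and ±tanh(1.96/√27) = ±0.36 at n = 30. A null-looking result would therefore remain compatible with a moderate association.

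**Step 6: the other reading.** If the ratings and HS-PGA are treated as continuous, section 6 provides mean and range only. Neither relates one variable to another.

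**The case against.** **Is the wrong test assigned?** A reader might infer that the plan assigns chi-squared/Fisher to the HS-PGA question. It does not. Section 4 names no method, section 6 does not list its categorical variables, and the test has proper nominal uses, such as dressing type by body part. The summed-score wording and the change-from-baseline endpoints also allow a numeric reading. This stands: the defect is a missing assignment. It does not remove the point, since one reading leaves an order-blind test and the other leaves none.

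**Would most real associations be missed?** A reader might also infer this, and it is too strong. The missed share depends on a strength of association and a spread of categories that the documents do not give. It falls to 35–39% at 0.7 and 12–16% at 0.8 with 30 subjects on the full scales. In 3 × 4 tables it is about 20–48% at 0.7.

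**Are full tables realistic?** Entry requires an actively draining lesion. If that lesion is an abscess or draining fistula, Clear and Minimal cannot occur at baseline. This limits the 4 × 6 argument at baseline, but not at week 6. Section 4 also treats a reduction of 2 or more HS-PGA points as a meaningful response. If that binary response were cross-tabulated with a three-level change, the missed share would be only 13–34%, although dichotomizing itself loses power.

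**Would a non-significant result be credited to the dressings?** No passage says so; it is a possible misreading, not a planned one. Nor would a change of test alone prevent it, because Spearman is also weak at small correlations. That is why the interval matters more than the p-value.

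**Is this a small matter?** The study is a pilot, and the correlation with HS-PGA is not a listed endpoint. That limits the weight of the point, though the correction is also small.

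**Conclusion.** The point holds in a limited form. The plan states an aim of correlating outcomes with disease progression and gives it no method. The one test it names does not use category order and cannot show direction. If that test is used on the full ordered scales at 20 to 30 subjects, power at an assumed latent correlation of about 0.5 is roughly 12–29%, against 49–75% for a rank test. These figures rest on an assumed two-sided 5% level, assumed category frequencies and a latent-normal model. The direction of the difference was the same in every simulated setting with a correlation of 0.3 or more, but its size varies with the number of occupied categories and the strength of association. This is a worthwhile correction to a secondary analysis and does not bear on the primary endpoint, change in DLQI.

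**What to change.** In section 6, add wording such as: *Associations between change in the sleep, drainage and odor ratings and change in HS-PGA, from baseline to week 6 with one row per subject, will be estimated with Spearman's rank correlation and its 95% confidence interval on the full scales. Conclusions will be drawn from the interval, and a non-significant result will not be taken as evidence of independence.* Keep chi-squared/Fisher for nominal variables, such as sex or dressing type, also with one row per subject. State whether HS-PGA is analyzed as the six-level rating or as a summed score. Using a single change per subject also avoids pooling the three visits as if they were independent.

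The cost is a few sentences, with no new data, visits or subjects. The downsides are that a rank correlation would miss a non-monotone pattern, which is not what section 4 asks about, and that at 20 to 30 subjects it remains imprecise for weak associations.

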8.1 Definition of Adverse events

An adverse event (AE) is any untoward medical occurrence (e.g., any unfavorable and unintended sign [including abnormal laboratory findings], symptom or disease) in a subject or clinical investigation subject after providing written informed consent for participation in the study. Therefore, an AE may or may not be temporally or causally associated with the use of a medicinal (investigational) product. In addition, all reports of intentional misuse and abuse of the product are also considered an adverse event irrespective if a clinical event has occurred. The investigator has the responsibility for managing the safety of individual subject and identifying adverse events. Qualified study personnel will be readily available to advise on trial related medical questions or problems. The occurrence of adverse

events must be sought by non-directive questioning of the subject at each visit during the study. Adverse events also may be detected when they are volunteered by the subject during or between visits or through physical examination findings, laboratory test findings, or other assessments. Adverse events must be recorded in the Adverse Events eCRF under the signs, symptoms or diagnosis associated with them, accompanied by the following information (as far as possible) (if the event is serious refer to Section 8.2):

1. The severity grade.
 - mild: usually transient in nature and generally not interfering with normal activities
 - moderate: sufficiently discomforting to interfere with normal activities
 - severe: prevents normal activities
2. its relationship to the study treatment (suspected: Yes/No). If the event is due to lack of efficacy or progression of underlying illness (i.e. progression of the study indication), the assessment of causality will usually be 'Not suspected'. The rationale for this guidance is that the symptoms of a lack of efficacy or progression of underlying illness are not caused by the trial drug, they happen in spite of its administration and/or both lack of efficacy and progression of underlying disease can only be evaluated meaningfully by an analysis of cohorts, not on a single subject.
3. its duration (start and end dates) or if the event is ongoing, an outcome of not recovered/not resolved must be reported.
4. whether it constitutes a serious adverse event (SAE - see Section 8.2 for definition of SAE) and which seriousness criteria have been met.
5. action taken regarding with study intervention.

All adverse events must be treated appropriately. Treatment may include one or more of the following:

- study dressing regime not changed
- study dressing regime interrupted/dressings withdrawn

Conditions that were already present at the time of informed consent should be recorded in medical history of the subject. Adverse events (including lab abnormalities that constitute AEs) should be described using a diagnosis whenever possible, rather than individual underlying signs and symptoms. Adverse event monitoring should be continued for at least 10 weeks following the last date of study dressing usage. Once an adverse event is detected, it must be followed until its resolution or until it is judged to be permanent (e.g. Continuing at the end of the study), and assessment must be made at each visit (or more frequently, if necessary) of any changes in severity, the suspected relationship to the interventions required to treat it, and the outcome.

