point likert scale. Quality of sleep, drainage, and odor will be assessed as well (Table 1). Photographs and measurements will be taken of wounds associated with HS. Any active wounds will receive standard of care, including cleaning and debridement to remove all nonviable soft tissue from the wound by scalpel, tissue nippers and/or curettes when appropriate. Wound swab samples will be collected from patients from one active wound at each visit. This site will be identified during the baseline visit. If debridement is indicated as part of standard care, prior to debridement of the wound, a wound swab sample will be collected from the wound bed. In circumstances where a layer of nonviable tissue is preventing swab collection, the swab sample should be collected during the course of the debridement process wherein the wound bed has been exposed. Subjects will be provided with a kit that will include 3 types of FDA-cleared dressings (1) Cutimed® Sorbact® Hydroactive B, 2) Cutimed® Siltec®, and, 3) Sorbion® Sana multi-star) that are available on the market and general wound care supplies (i.e. tape, gauze) that are also FDA-cleared and available on the market. Dressing instructions involve applying desired dressing daily to affected areas and securing with tape as needed. Participants may change dressings as needed. Instructions will be reviewed with participants upon enrollment. Participating subjects will also be given a 2-week log where they will be instructed to fill in which dressings they used on which wounds, and how often they changed the dressings.

Subjects will receive weekly phone calls in between follow ups (for a total of 4 phone calls) by the research team where they will be asked to answer questions on average and maximal pain, quality of sleep, drainage and odor. Subjects will be asked to follow up in 14 +/- 3 days from visit 0 (visit 1), at which point the physical exam will be performed. Maximal and average pain will again be assessed on a 5-point likert scale. Quality of sleep, drainage, and odor will be assessed as well (Table 1). Photographs and measurements of HS wounds will be taken and the dressing logs will be collected and evaluated. Wound swab samples will be collected from the wound that was pre-identified at baseline visit. Participants will share with study personnel which dressings were most useful to them, and this will dictate the dressing type that each subject receives for the remaining 4 weeks of the study period.

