Appendix Table 1. Hidradenitis Suppurativa Physician's Global Assessment Scale

Rating	Description
Clear	0 abscesses, 0 draining fistulas, 0 inflammatory nodules, and 0 noninflammatory nodules
Minimal	0 abscesses, 0 draining fistulas, 0 inflammatory nodules, and presence of noninflammatory nodules
Mild	0 abscesses, 0 draining fistulas, and 1–4 inflammatory nodules or 1 abscess or draining fistula and 0 inflammatory nodules
Moderate	0 abscesses, 0 draining fistulas, and ≥ 5 inflammatory nodules or 1 abscess or draining fistula and ≥ 1 inflammatory nodule or 2–5 abscesses or draining fistulas and < 10 inflammatory nodules
Severe	2–5 abscesses or draining fistulas and ≥ 10 inflammatory nodules
Very severe	> 5 abscesses or draining fistulas

Table 1: Schedule of Events

	Baseline Visit Day 0	Phone call 1 Day 7	Follow-Up Visit Day 14	Phone call 2 Day 21	Phone call 3 Day 28	Phone call 4 Day 35	End of Treatment Visit Up to Day 42 after Baseline Visit
Visit Window		7 +/- 3 Days from Baseline Visit	14 +/- 3 Days from Baseline Visit	7 +/- 3 Days from Follow-Up Visit	14 +/- 3 Days from Follow-Up Visit	21 +/- 3 Days from Follow-Up Visit	28 +/- 3 Days from Follow-Up Visit
Visit #	0		1				2
Informed Consent/PHI authorization	X						
Demographics	X						
Medical History ^A	X						
Concomitant Medications & Procedures Assessment	X		X				X
Physical Exam ^B	X		X				X
Inclusion/Exclusion Determination	X						
Wound(s) Photograph	X		X				X
Dermatology Life Quality Index (DLQI)	X						X
Average 24 hours pain Score (NRS)	X	X	X	X	X	X	X
Maximal 24 hours pain Score (NRS)	X	X	X	X	X	X	X
Review Dressing Logs			X				X
Sleep assessment	X	X	X	X	X	X	X
Drainage assessment	X	X	X	X	X	X	X

Dressing Satisfaction	X		X				X
Dressings' Ease of Use	X		X				X
Odor assessment	X	X	X	X	X	X	X
HS-PGA	X		X				X
Wound Swab Sample Collection	X		X				X
Adverse Events Assessment			X				X

A: Detailed HS history will be gathered, including current wound care regime (types and number of dressings utilized per week, including an estimate of anticipated dressings needed per week), exacerbating and alleviating factors; B: Hurley staging will be assessed, as well as types (inflammatory, sinus tracts, ulcerations), number, and location of lesions

5) Data and Specimen Banking*

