8.3 SAE reporting

To ensure subject safety, every SAE, regardless of causality, occurring after the subject has provided informed consent and until 10 weeks following the last administration of study dressings must be reported within 24 hours of learning of its occurrence.

All follow-up information for the SAE including information on complications, progression of the initial SAE and recurrent episodes must be reported as follow-up to the original episode within 24 hours of the investigator receiving the follow-up information. An SAE occurring at a different time interval or otherwise considered

completely unrelated to a previously reported one must be reported separately as a new event.

If the SAE is not previously documented (new occurrence) and is thought to be related to the study treatment, a CMO & PS Department associate may urgently require further information from the investigator for health authority reporting.

Suspected Unexpected Serious Adverse Reactions (SUSARs) will be collected and reported to the competent authorities and relevant ethics committees in accordance with EU Guidance 2011/C 172/01 or as per national regulatory requirements in participating countries. Any SAEs experienced after the 10 week period following the last administration of study treatment should only be reported if the investigator suspects a causal relationship to study treatment. Any SAEs reported up to the subject's last visit will be reported in the AE eCRF. SAEs beyond that date will only be recorded in the Safety database.

Risks to subjects in this study include contact dermatitis in the skin areas exposed to the dressings provided in this study. However, we will be utilizing FDA-cleared dressings that are available on the market and therefore pose a risk that is no higher than the current risk subjects are undertaking while utilizing other dressings over the same skin areas.

8) Potential Benefits to Subjects*

Direct benefits to subjects include complimentary access to various high quality dressings that they might otherwise not have had access to as they may not be covered by insurance for HS.

9) Vulnerable Populations*

Pregnant women, prisoners, and children younger than 18 years old are excluded.

10) Setting

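### Adverse event monitoring is promised for 10 weeks after last dressing use, but contact ends at about day 42, and adverse events are asked about at only 2 of 6 post-baseline contacts

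*Combined protocol and SAP*

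**What the plan says.** **Length of monitoring.** Section 8.1 states: "Adverse event monitoring should be continued for at least 10 weeks following the last date of study dressing usage". Section 8.3 uses the same 10 weeks for reporting serious adverse events (SAEs), with the 24-hour clock starting when the event becomes known. For SAEs after the subject's last visit it says "SAEs beyond that date will only be recorded in the Safety database".

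**Scheduled contacts.** Section 4 describes three visits over six weeks, and the last column of Table 1 is headed "End of Treatment Visit Up to Day 42 after Baseline Visit". No later visit, call or record review appears.

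**How events are found.** Under Section 8.1, adverse "events must be sought by non-directive questioning of the subject at each visit during the study". It then adds: "Adverse events also may be detected when they are volunteered by the subject during or between visits". Examination findings and other assessments also count.

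**What is asked, and when.** In Table 1 the row "Adverse Events Assessment" is marked at Visit 1 (day 14) and Visit 2 (day 42) and is blank for all four calls. Section 4 says that on the calls subjects are "asked to answer questions on average and maximal pain, quality of sleep, drainage and odor".

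**Risk and drop-out.** The end of Section 8.3 says: "Risks to subjects in this study include contact dermatitis in the skin areas exposed to the dressings provided in this study". Section 14 aims for 20 subjects and enrols 30 because many are expected to drop out. Table 1 has no early-termination visit.

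**The concern.** There are two separate points.

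1. The monitoring period in Section 8.1 is longer than the schedule can deliver. After the end-of-treatment visit nobody is due to ask the subject anything, so non-serious events are found only if volunteered. A report stating that adverse events were monitored for 10 weeks after use would describe something that was not actively done.

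2. Active questioning is thin while the dressings are worn, which is when contact dermatitis would arise. After Visit 1 each subject goes on with the dressing type found most useful and is telephoned three times before Visit 2, with no adverse event question in that interval. A subject who leaves before Visit 1 is never asked about adverse events, and one who leaves between Visits 1 and 2 is not asked again. If the reason for leaving was a skin reaction, that reaction may go unrecorded, and it is the tolerability information a dressing study most needs.

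**Working it through.** The check is calendar arithmetic and a count of Table 1 columns.

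**Inputs**
- Monitoring after last use: 10 weeks = 70 days (Section 8.1).
- Visit 1: day 14 ± 3, so days 11 to 17 (Section 4, Table 1).
- Visit 2: 28 ± 3 days after Visit 1, so 25 to 31 days later (Section 4, Table 1).
- Calls: nominal days 7, 21, 28 and 35. Call 1 is at 7 ± 3 days from baseline; calls 2 to 4 are at 7, 14 and 21 days from Visit 1, each ± 3 (Table 1).
- Enrolment 30, target 20 (Section 14).

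**Last scheduled contact**
- Nominal: 14 + 28 = day 42.
- Earliest: 11 + 25 = day 36.
- Latest: day 42 if the Table 1 column heading is read as a cap; 17 + 31 = day 48 if only the windows apply.

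**End of the 10-week period when dressings are used until Visit 2**
- Nominal: 42 + 70 = day 112.
- Range: 36 + 70 = 106 to 42 + 70 = 112 with the cap, or to 48 + 70 = 118 without it.
- Share of the nominal 112 days that falls after the last contact: 70 / 112 = 62.5%.

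**Earlier last use, with Visit 2 attended on day 42**

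For last use on day *d*, the period ends on day *d* + 70, so the shortfall after day 42 is *d* + 70 − 42 = *d* + 28.

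| Last use (day) | Period ends (day) | Days after last contact |
|---|---|---|
| 0 | 70 | 28 |
| 14 | 84 | 42 |
| 28 | 98 | 56 |
| 35 | 105 | 63 |
| 42 | 112 | 70 |

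The shortfall is 28 to 70 days, so the day 42 visit never completes the period. With Visit 2 on day 48, last use on day 0 would still leave 70 − 48 = 22 days uncovered.

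**Frequency of adverse event questions**
- Post-baseline contacts: 4 calls + 2 visits = 6. Contacts with adverse event assessment: 2.
- Interval between those two: 42 − 14 = 28 days nominal, 25 to 31 with the window.
- If the calls also ask: 6 of 6 contacts, 7 days apart nominally. The longest gap that the windows allow is 13 days (for example call 1 on day 4 and Visit 1 on day 17: 17 − 4 = 13).

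**Drop-out allowance:** 30 − 20 = 10 subjects; 10 / 30 = 33%.

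**The case against.** The strongest reply is that Section 8.1 asks for monitoring to continue and does not promise scheduled contacts. Volunteered reports are a listed route of detection, and SAEs after day 42 would come to light in the same passive way. The named risk largely ends when the dressings come off, so the 70 days are not the period of greatest interest.

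On the calls, Section 8.1 requires questioning at visits, and Table 1 provides it at both post-baseline visits. Weekly calls give subjects a chance to mention a rash. The visits include examination, photographs and a concomitant medication review, so a persisting reaction should be seen. The 33% is a recruitment allowance, and nothing in the protocol ties drop-out to skin reactions. Section 8.1 also provides for interrupting or withdrawing dressings and for following a detected event until it resolves.

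Much of this stands:
- The missing question on the calls is a weakness, not a breach of Section 8.1.
- Section 8.3 is not in conflict with the schedule, because it applies once an SAE is known.
- The late uncovered period matters less for contact dermatitis than the weeks of use.
- That drop-out would be linked to reactions is plausible but not shown.

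It does not remove the point. Section 8.1 makes questioning obligatory and volunteered reports an addition to it, and after day 42 only the addition is left. The rule on following events to resolution helps only once an event has been found. No provision makes staff ask a subject who stops attending.

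**Conclusion.** Both parts hold. The monitoring period in Section 8.1 outlasts the schedule by 70 days for a subject who uses dressings to day 42, and by 28 to 70 days for any last use from day 0 to day 42 when Visit 2 falls on day 42. Reading the Visit 2 window as reaching day 48 does not change the conclusion. Adverse events are actively sought at 2 of 6 post-baseline contacts, nominally 28 days apart, with no question tied to withdrawal.

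The first part is a mismatch between text and schedule; the second is an opportunity to improve ascertainment. The consequences are modest: the dressings are FDA-cleared, this is a 30-subject pilot, safety is not a listed endpoint, and neither the DLQI result nor any other planned endpoint changes. The change should be made because it improves capture of dressing tolerability at very little cost and makes the stated monitoring period true.

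**What to change.** 1. In Table 1, mark adverse event assessment for calls 1 to 4, and add one non-directive adverse event question to the call script.
2. Ask the same question at the last contact with any subject who withdraws.
3. Bring Section 8.1 into line with the schedule in one of two ways, for the sponsor to choose:
   - end the adverse event monitoring period at the end-of-treatment visit. Section 8.3 can stay as it is, with the consequence that later SAEs are still found only passively; or
   - keep the 10 weeks and add one brief closing call about 10 weeks after last dressing use (about day 112 for a subject who uses dressings to day 42).

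The cost is one question on calls already planned, an edit to one row of Table 1 and one sentence in Section 8.1. Calls become slightly longer. The second option adds one call per subject, at most 30 in all.
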